### Examples of Eligible Gating and Residual Function Mutations

711+3A>G	L206W	K1060T
2789+5G>A	R347H	A1067T
3272-26A>G	R352Q	G1069R
3849+10kbC>T	A455E	R1070Q
E56K	S549N	R1070W
P67L	S549R	F1074L
R74W	G551D	D1152H
D110E	G551S	G1244E
D110H	D579G	S1251N
R117C	E831X	S1255P
R117H	S945L	D1270N
G178R	S977F	G1349D
E193K	F1052V	

### *CFTR* Mutations Responsive to ELX/TEZ/IVA Based on In Vitro Data

3141del9	E822K	G1244E	L997F	R117P	S945L
546insCTA	F191V	G1249R	L1077P	R170H	S977F
A46D	F311del	G1349D	L1324P	R258G	S1159F
A120T	F311L	H139R	L1335P	R334L	S1159P
A234D	F508C	H199Y	L1480P	R334Q	S1251N
A349V	F508C;S1251N †	H939R	M152V	R347H	S1255P
A455E	F575Y	H1054D	M265R	R347L	T338I
A554E	F1016S	H1085P	M952I	R347P	T1036N
A1006E	F1052V	H1085R	M952T	R352Q	T1053I
A1067T	F1074L	H1375P	M1101K	R352W	V201M
D110E	F1099L	I148T	P5L	R553Q	V232D
D110H	G27R	I175V	P67L	R668C	V456A
D192G	G85E	I336K	P205S	R751L	V456F
D443Y	G126D	I502T	P574H	R792G	V562I
D443Y;G576A;R668C †	G178E	I601F	Q98R	R933G	V754M
D579G	G178R	I618T	Q237E	R1066H	V1153E
D614G	G194R	I807M	Q237H	R1070Q	V1240G
D836Y	G194V	I980K	Q359R	R1070W	V1293G
D924N	G314E	I1027T	Q1291R	R1162L	W361R

***CFTR* Mutations Responsive to ELX/TEZ/IVA Based on In Vitro Data**

D979V	G463V	I1139V	R31L	R1283M	W1098C
D1152H	G480C	I1269N	R74Q	R1283S	W1282R
D1270N	G551D	I1366N	R74W	S13F	Y109N
E56K	G551S	K1060T	R74W;D1270N †	S341P	Y161D
E60K	G576A	L15P	R74W;V201M †	S364P	Y161S
E92K	G576A;R668C †	L165S	R74W;V201M;D1270N †	S492F	Y563N
E116K	G622D	L206W	R75Q	S549N	Y1014C
E193K	G628R	L320V	R117C	S549R	Y1032C
E403D	G970D	L346P	R117G	S589N	
E474K	G1061R	L453S	R117H	S737F	
E588V	G1069R	L967S	R117L	S912L	

† Complex/compound mutations where a single allele of the *CFTR* gene has multiple mutations; these exist independent of the presence of mutations on the other allele.

## **2                    MODIFICATIONS**

### **2.1                Modifications to the Approved Clinical Study Protocol**

Not Applicable.

### **2.2                Modifications to the Approved Statistical Analysis Plan**

This is the first version of the Statistical Analysis Plan.

### **2.3                Modifications to the Approved DMC Charter**

Not Applicable.

### **3 INTRODUCTION**

This statistical analysis plan (SAP) is the planned statistical analysis for Study VX20-121-103 (Study 103) and is based on the most recent approved clinical study protocol (CSP), the most recent approved electronic case report form (eCRF), and the most recent eCRF completion guidelines.

Study 103 is a Phase 3, randomized, double-blind, elexacaftor/tezacaftor/ivacaftor (ELX/TEZ/IVA)-controlled, parallel group, multicenter study evaluating the efficacy and safety of vanzacaftor (VX-121)/tezacaftor/deutivacaftor (VNZ/TEZ/D-IVA) in cystic fibrosis (CF) subjects who are homozygous for *F508del* (F/F), heterozygous for *F508del* and a gating (F/G) or residual function (F/RF) mutation, or have at least 1 triple combination responsive (TCR) *CFTR* mutation identified as responsive to ELX/TEZ/IVA and do not have an *F508del* mutation (TCR/non-F). This SAP (Methods) documents the planned final analyses and data presentation for Study 103. For some of these analyses, the Study 103 data are pooled with data from Study VX20-121-102 (Study 102) which is running in parallel with a similar study design and aims to evaluate similar outcomes using a different patient population.

The Vertex Pharmaceuticals Incorporated (Vertex) Biometrics Department will perform the statistical analysis of the efficacy and safety data. SAS® Version 9.4 Software (SAS Institute, Cary, North Carolina, USA) or higher will be used to generate all statistical outputs (tables, figures, listings, and datasets).

The SAP (Methods) will be finalized and approved prior to clinical database lock and treatment unblinding. Any revisions to the approved SAP will be documented and approved in an amendment to the SAP prior to the clinical database lock.

The analysis addressing the pharmacokinetic (PK) objective of the study will be described in the Clinical Pharmacology Analysis Plan which will be developed separately by the Clinical Pharmacology department at Vertex.

### **4 STUDY OBJECTIVES**

#### **4.1 Primary Objective**

To evaluate the efficacy of VNZ/TEZ/D-IVA in CF subjects who are homozygous for *F508del*, heterozygous for *F508del* and a gating (F/G) or residual function (F/RF) mutation, or have at least 1 other TCR *CFTR* mutation and no *F508del* mutation

#### **4.2 Secondary Objectives**

- To evaluate the safety of VNZ/TEZ/D-IVA
- To evaluate the PK of VNZ/TEZ/D-IVA

### **5 STUDY ENDPOINTS**

#### **5.1 Primary Endpoint**

Absolute change from baseline in percent predicted forced expiratory volume in 1 second (ppFEV1) through Week 24

## 5.2 Key Secondary Endpoints

- Absolute change from baseline in sweat chloride (SwCl) through Week 24
- Proportion of subjects with SwCl <60 mmol/L through Week 24 (pooled with data from Study 102)
- Proportion of subjects with SwCl <30 mmol/L through Week 24 (pooled with data from Study 102)

## 5.3 Other Secondary Endpoints

- Number of pulmonary exacerbations (PEX) through Week 52
- Absolute change from baseline in Cystic Fibrosis Questionnaire – Revised (CFQ-R) Respiratory Domain (RD) score through Week 24
- Absolute change from baseline in ppFEV1 through Week 52
- Absolute change from baseline in SwCl through Week 52
- Proportion of subjects with SwCl <60 mmol/L through Week 24
- Proportion of subjects with SwCl <30 mmol/L through Week 24
- Safety and tolerability assessments based on adverse events (AEs), clinical laboratory values, electrocardiograms (ECGs), vital signs, and pulse oximetry

## 5.4 Other Endpoints

[figure not shown]
- Proportion of subjects with SwCl <60 mmol/L through Week 52
- Proportion of subjects with SwCl <30 mmol/L through Week 52
- Absolute change from baseline in body mass index (BMI) at Week 52
- Absolute change from baseline in BMI z-score at Week 52
- Absolute change from baseline in weight at Week 52
- Absolute change from baseline in CFQ-R RD score through Week 52
- PK parameters of VNZ, TEZ, and D-IVA

## 6 STUDY DESIGN

### 6.1 Overall Design

Study 103 is a Phase 3, randomized, double-blind, ELX/TEZ/IVA-controlled, parallel-group, multicenter study. A schematic of the study design is provided in [Figure 6-1](#).

**Figure 6-1 Schematic View of the Study Design**

D-IVA: deutivacaftor; ELX: elexacaftor; IVA: ivacaftor; TEZ: tezacaftor; VNZ: vanzacaftor  
 Note: The figure is not drawn to scale.

Approximately 550 subjects will be enrolled and randomized.

All subjects entering the Run-in Period will receive ELX 200 mg once daily (qd)/TEZ 100 mg qd/IVA 150 mg every 12 hours (q12h). Following completion of the Run-in Period, subjects will be randomized (1:1) to the VNZ/TEZ/D-IVA group or the ELX/TEZ/IVA group for the Treatment Period. The dosages to be evaluated are shown in Table 6-1. Randomization will be stratified; details are provided in 6.3.

**Table 6-1 Treatment Groups and Dosages**

Treatment Group	VNZ	ELX	TEZ	D-IVA	IVA
VNZ/TEZ/D-IVA	20 mg qd	0 mg	100 mg qd	250 mg qd	0 mg
ELX/TEZ/IVA	0 mg	200 mg qd	100 mg qd	0 mg	150 mg q12h

D-IVA: deutivacaftor, ELX: elexacaftor, IVA: ivacaftor; q12h: every 12 hours; qd: once daily; TEZ: tezacaftor; VNZ: vanzacaftor

## 6.2 Sample Size and Power

### 6.2.1 Power for Primary Analysis of Primary Efficacy Endpoint

The primary efficacy endpoint is the absolute change from baseline in ppFEV1 through Week 24. The primary null hypothesis to be tested is that the mean absolute change in ppFEV1 from baseline through Week 24 for VNZ/TEZ/D-IVA is inferior by >3 percentage points compared to ELX/TEZ/IVA.

The non-inferiority margin represents a clinically acceptable loss of effectiveness as outlined in regulatory guidances. Furthermore, a statistical approach using the Rothmann method recommends that the non-inferiority margin preserve at least 50% of the treatment effect of the active control (ELX/TEZ/IVA) compared to placebo, where the treatment effect is estimated by the lower bound of the 95% confidence interval (CI). In the overall population eligible for this

study, the lower bound of the 95% CI of the treatment effect for ELX/TEZ/IVA is approximately 12 percentage points for ppFEV1. The selected non-inferiority margin of 3 percentage points is consistent with this statistical method and the non-inferiority margin for ppFEV1 used in clinical studies evaluating symptomatic CF treatments.

The null hypothesis will be tested at a 1-sided significance level of 0.025.

Assuming a within-group standard deviation (SD) of 8 and a 10% drop-out rate at Week 24 and a treatment difference of 0 between VNZ/TEZ/D-IVA and ELX/TEZ/IVA, a sample size of 275 subjects in each group for a total of 550 subjects will have more than 95% power to test the primary hypothesis for the primary endpoint, based on a 1-sided, 2-sample *t*-test at a significance level of 0.025.

### **6.2.2 Power for Analysis of Selected Key Secondary Efficacy Endpoint**

A key secondary efficacy endpoint is the absolute change from baseline in SwCl through Week 24. Assuming a within-group SD of 14 mmol/L and a 10% drop-out rate at Week 24, a sample size of 275 subjects in each treatment group will have more than 95% power to detect a difference between the treatment groups of -5 mmol/L for the absolute change from baseline in SwCl through Week 24, based on a 2-sided, 2-sample *t*-test at a significance level of 0.05.

### **6.3 Randomization**

Approximately 550 subjects will be randomized (1:1) to the VNZ/TEZ/D-IVA group or the ELX/TEZ/IVA group. Randomization will be stratified by age at the Screening Visit (<18 versus ≥18 years of age), ppFEV1 determined during the Run-in Period (Day -14 clinic assessment; <70 versus ≥70 percentage points), SwCl determined during the Run-in Period (Day -14 assessment; <30 versus ≥30 mmol/L), prior CFTR modulator use (yes versus no), and genotype group (F/F, F/G, F/RF, and TCR/non-F).

### **6.4 Blinding and Unblinding**

This is a double-blind study. Please refer to Section 10.7 of the Study 103 CSP for details.

## **7 ANALYSIS SETS**

### **7.1 All Subjects Set**

The **All Subjects Set** will include all subjects who were randomized or received at least 1 dose of study drug. This analysis set will be used for all individual subject data listings and disposition summary tables, unless otherwise specified.

### **7.2 Full Analysis Set**

The **Full Analysis Set** (FAS) will include all randomized subjects who carry the intended *CFTR* genotype and received at least 1 dose of study drug during the Treatment Period. The FAS will be used to summarize subject demographics and baseline characteristics and for analyses of all efficacy endpoints in which subjects will be analyzed according to their randomized treatment group, unless otherwise specified.

### **7.3 Pooled Full Analysis Set**

The **Pooled Full Analysis Set** (PFAS) will include all randomized subjects from this study (Study 103) and from Study 102 who carry the intended *CFTR* genotype and received at least 1

dose of study drug during the Treatment Period. The PFAS will be used only for pooled analysis of selected endpoints.

#### **7.4 Safety Set**

The **Safety Set for the Run-in Period** will include all subjects who received at least 1 dose of ELX/TEZ/IVA during the Run-in Period. This safety set will be used for safety-related outputs during the Run-in Period, unless otherwise specified.

The **Safety Set for the Treatment Period** will include all subjects who received at least 1 dose of study drug during the Treatment Period. This safety set will be used for all safety analyses during the Treatment Period in which subjects will be analyzed according to the treatment they actually received, unless otherwise specified.

### **8 STATISTICAL ANALYSIS**

#### **8.1 General Considerations**

The Schedule of Assessments is provided in the CSP for Study 103. The precision standards for reporting safety and efficacy variables are provided in an internal Biometrics document that specifies the programming rules including the precision for derived variables.

**Continuous variables** will be summarized using the following descriptive summary statistics: the number of subjects (n), mean, SD, median, minimum value (min), and maximum value (max).

**Categorical variables** will be summarized using counts and percentages. Percentages will be presented to 1 decimal place.

#### **Baseline value:**

For all safety endpoints:

- Unless otherwise specified, baseline will be defined as the most recent non-missing measurement (scheduled or unscheduled) collected before the first dose of study drug in the Treatment Period (i.e., the Day 1 Visit).

For all efficacy endpoints:

- Except for SwCl, baseline will be defined as the pre-dose Day 1 value. If the pre-dose Day 1 value is missing, the most recent pre-dose, non-missing value on or after the Day -14 visit, including unscheduled visits, will be used as baseline.
- For SwCl, baseline will be defined as the average of the two most recent pre-dose, non-missing values on or after the Day -14 visit, including unscheduled visits. If only 1 non-missing value is available during this interval, the available value will be considered as baseline.

**Absolute change** from baseline will be calculated as post-baseline value - baseline value.

**Relative change** from baseline will be calculated as (post-baseline value - baseline value)/baseline value.

The **Treatment-emergent (TE) Period for the Run-in Period** will be from the first dose date of study drug in the Run-in Period to (1) the first dose date of study drug in the Treatment Period for subjects who complete the Run-in Period and continue to the Treatment Period, or (2) 28 days after the last dose date of study drug in the Run-in Period or to the completion of study participation date, whichever occurs first, for subjects who do not continue to the Treatment Period (e.g., subjects who do not meet the conditions to enter the Treatment Period).

The **TE Period for the Treatment Period** will be from the first dose date of study drug in the Treatment Period (VNZ/TEZ/D-IVA or ELX/TEZ/IVA) to 28 days after the last dose date of study drug in the Treatment Period or to the completion of study participation date, whichever occurs first.

The **PEx analysis period through Week 52** will be from the first dose date of study drug in the Treatment Period to the last efficacy assessment, which may be collected up to the Week 52 Visit or the earlier of Day 365 and the completion of study participation date if a subject does not have the Week 52 Visit.

**Unscheduled visits:** Unscheduled visit measurements will be included in analysis as follows:

- 1) In scheduled visit windows per specified visit windowing rules
- 2) In the derivation of baseline and last on-treatment measurements
- 3) In the derivation of maximum and minimum values and maximum and minimum change from baseline values during the TE Period for the Treatment Period for safety analyses
- 4) In individual subject data listings as appropriate

**Visit windowing rules:** The analysis visit windows for protocol-defined visits are provided in [Appendix](#).

**Incomplete/missing data:** Details on how to handle missing data are described in subsequent sections when applicable.

**Outliers:** No formal statistical analyses will be performed to detect or remedy the presence of statistical outliers, unless otherwise specified.

**Multiplicity:** The multiplicity adjustment procedure for the primary and key secondary endpoints is described in [8.3.2.3](#). All other *P* values are nominal.

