**Treatment Groups and Dosages**

Treatment Group	VX-121	ELX	TEZ	D-IVA	IVA
VX-121/TEZ/D-IVA	20 mg qd	0 mg	100 mg qd	250 mg qd	0 mg
ELX/TEZ/IVA	0 mg	200 mg qd	100 mg qd	0 mg	150 mg q12h

D-IVA: deutivacaftor; ELX: elexacaftor; IVA: ivacaftor; q12h: every 12 hours; qd: once daily; TEZ: tezacaftor

- Assessments**
  - Efficacy:** Spirometry, SwCl, CFQ-R, documentation of events related to health outcomes (e.g., PEx), height, and weight
  - Safety:** AEs, clinical laboratory assessments, ECGs, vital signs, pulse oximetry, physical examinations, and ophthalmologic examinations (for subjects <18 years of age on the date of informed consent)
  - PK:** VX-121, TEZ, D-IVA, ELX, IVA, and relevant metabolite plasma concentrations
  - Exploratory:** Treatment Satisfaction Questionnaire for Medication (TSQM), Cystic Fibrosis Impact Questionnaire (CF-IQ), DNA sample (optional), inflammatory mediators, blood biomarker sample, RNA sample (optional), and sputum samples

**Statistical Analyses** The primary efficacy endpoint is the absolute change from baseline in ppFEV1 through Week 24 (estimated by averaging Weeks 16 and 24). The primary null hypothesis to be tested is that the mean absolute change from baseline in ppFEV1 through Week 24 for VX-121/TEZ/D-IVA is inferior by >3 percentage points compared to ELX/TEZ/IVA. The null hypothesis will be tested at a 1-sided significance level of 0.025.

Assuming a within-group SD of 8 and 10% drop-out rate at Week 24 and a treatment difference of 0 between VX-121/TEZ/D-IVA and ELX/TEZ/IVA, a sample size of 275 subjects in each group for a total of 550 subjects will have more than 95% power to test the primary hypothesis for the primary endpoint, based on a 1-sided, 2-sample *t*-test at a significance level of 0.025.

The primary analysis of the primary endpoint will be conducted with clinic spirometry data only and will be performed using a mixed-effects model for repeated measures (MMRM) with absolute change from baseline in ppFEV1 at Day 15, Week 4, Week 8, Week 16, and Week 24 as the dependent variable. The model will include treatment group, visit, and treatment-by-visit interaction as fixed effects, with continuous baseline ppFEV1, continuous baseline SwCl, age at screening (<18 versus ≥18 years of age), and genotype group (F/F, F/G, F/RF, and TCR/non-F) as covariates. An unstructured covariance structure will be used to model the within-subject errors.

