**Table 3-2 Study VX20-121-103: Run-in Period, Treatment Period, and Safety Follow-up Visit**

Event/Assessment a	Run-in Period		Treatment Period b						ETT Visit c	Safety Follow-up Visit 28 (± 7) Days After the Last Dose of Study Drug (If Applicable) d	Comments
	Day -28 (± 1 Day)	Day -14 (Day -15 to Day -3)	Day 1	Day 15 (± 3 Days)	Weeks 4, 8, 12, 16 (± 5 Days)	Weeks 20, 28, 32, 40, 44, 48 (± 5 Days)	Weeks 24 and 36 (± 5 Days)	Week 52 (± 5 Days)			
Clinic visit	X	X	X	X	X e		X	X	X	X	See Section 9.1.8 for use of remote measures in extenuating circumstances.
Telephone contact						X					Assess the subject’s status, any AEs, concomitant medications, treatments, and procedures.
Inclusion and exclusion criteria review	X										Section 8
Randomization			X								Randomization may occur on either Day -1 or Day 1, after all eligibility criteria are confirmed (Section 9.1.3).
CFQ-R			X		Weeks 8 and 16		Week 24	X	X		Completed before the start of any other assessments on the day of the study visit (Section 11.5.3).

a All assessments will be performed before dosing unless noted otherwise.

b To enter the Treatment Period, conditions for entry must be satisfied (Section 9.1.3).

c If the subject prematurely discontinues study drug treatment, an ETT Visit should be scheduled as soon as possible after the decision to discontinue treatment (Section 9.1.5). Subjects who prematurely discontinue treatment during the Run-in Period will complete an ETT Visit and Safety Follow-up Visit, as applicable. Subjects who prematurely discontinue study drug treatment during the Treatment Period should continue to complete all scheduled study visits for assessments following completion of the ETT Visit (and Safety Follow-up Visit, if applicable).

d The Safety Follow-up Visit is required for all subjects, unless otherwise specified (Section 9.1.4). For subjects who complete an ETT Visit 3 weeks or later following the last dose of study drug, the ETT Visit will replace the Safety Follow-up Visit, and a separate Safety Follow-up Visit will not be required (Section 9.1.5).

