### **9.1.2 ELX/TEZ/IVA Run-in Period**

The Run-in Period has a 4-week duration and is designed to establish a reliable on-treatment (ELX/TEZ/IVA) baseline for the Treatment Period. The first dose of open-label ELX/TEZ/IVA will be administered at the Day -28 Visit. Female subjects must have a negative pregnancy test at Day -28 before receiving study drug. The last dose of open-label ELX/TEZ/IVA will be administered on Day -1 (1 day before the Day 1 Visit).

On Day -14, spirometry (clinic and mobile) and SwCl will be assessed. The Day -14 clinic spirometry and SwCl assessments will be used for stratification of randomization (Section 9.2).

Subjects who prematurely discontinue study drug treatment during the Run-in Period will not be randomized or participate in the Treatment Period (Section 9.1.5.1).

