##### **12.3.3.1 Analysis of Primary Endpoint**

The primary efficacy endpoint is the absolute change from baseline in ppFEV1 through Week 24 (estimated by averaging Weeks 16 and 24). The primary analysis will be conducted with clinic spirometry data only and will be performed using a mixed-effects model for repeated measures

(MMRM) with absolute change from baseline in ppFEV1 at Day 15, Week 4, Week 8, Week 16, and Week 24 as the dependent variable. The model will include treatment group, visit, and treatment-by-visit interaction as fixed effects, with continuous baseline ppFEV1, continuous baseline SwCl, age at screening (<18 versus ≥18 years of age), and genotype group (F/F, F/G, F/RF, TCR/non-F) as covariates; if there is non-convergence due to small number of subjects in either F/G, F/RF, or TCR/non-F, the genotype group will be considered with two levels: F/F and non-F/F. The model will be estimated using restricted maximum likelihood. Denominator degrees of freedom for the F test for fixed effects will be estimated using the Kenward-Roger approximation. An unstructured covariance structure will be used to model the within-subject errors. If the model estimation does not converge, a compound symmetry covariance structure will be used instead. Conditional on the observed data and covariates, missing data will be assumed to be missing at random; therefore, no imputation of missing data will be performed.

The primary result obtained from the model will be the estimated treatment difference through Week 24. The adjusted mean with a 2-sided 95% CI will be provided. The primary null hypothesis will be rejected and non-inferiority demonstrated if the lower bound of the 95% CI is ≥-3.0. The estimated within group change from baseline and the treatment difference at each post-baseline visit will also be provided, obtained from the model.

The primary null hypothesis of non-inferiority described above will be tested based on the FAS.

If the lower bound of the 95% CI is greater than 0, then superiority for the primary endpoint is demonstrated and the 2-sided *P* value for superiority will be calculated.

Sensitivity analyses for handling missing data will be described in the SAP.

Supportive analyses and subgroup analyses (as appropriate) will also be described in the SAP.

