### 8.3.1.3 Primary Analysis

The primary null hypothesis to be tested is that the mean for the primary efficacy variable for VNZ/TEZ/D-IVA is inferior by >3 percentage points compared to ELX/TEZ/IVA. The primary analysis of the primary estimand will be performed using a mixed-effects model for repeated measures (MMRM) with change from baseline at Day 15, Week 4, Week 8, Week 16, and Week 24 as the dependent variable. The model will include fixed categorical effects for treatment, visit, age at screening (<18 versus ≥18 years of age), genotype group (F/F, F/G, F/RF, TCR/non-F), and treatment-by-visit interaction, with baseline ppFEV1 and baseline SwCl as continuous covariates. The model will be estimated using restricted maximum likelihood. Denominator degrees of freedom for the *F*-test for fixed effects will be estimated using the Kenward-Roger approximation. An unstructured covariance structure will be used to model the within-subject errors. If the model estimation does not converge, genotype group will be considered with two levels (F/F and non-F/F) or removed from the model, and if non-convergence persists, an alternative covariance structure like compound symmetry will be used. Conditional on the observed data and covariates, missing data will be assumed to be missing at random (MAR).

The primary result obtained from the model will be the estimated treatment difference through Week 24 (estimated by averaging Weeks 16 and 24). The adjusted mean with a 2-sided 95% CI and the 1-sided *P* value for non-inferiority will be provided. The primary null hypothesis will be rejected, and non-inferiority demonstrated, if the lower bound of the CI is ≥-3.0.

The primary null hypothesis of non-inferiority described above will be tested based on the FAS.

If non-inferiority for the primary endpoint is demonstrated, and if the lower bound of the same 95% CI is greater than 0, then superiority for the primary endpoint is also demonstrated, and the 2-sided *P* value for superiority will be presented.

The estimated within-group change from baseline and treatment difference at each post-baseline visit, obtained from the model, will be provided. The estimated within-group change and its standard error (SE) at each post-baseline visit will also be plotted by treatment group.

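### Optional precision gain: the primary ppFEV1 model omits the Day -14 on-treatment clinic value already collected; adding it would narrow the 95% CI by about 0% to 17%, a size the documents do not determine

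*SAP*

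**What the plan says.** SAP 8.1 sets the efficacy baseline: "Except for SwCl, baseline will be defined as the pre-dose Day 1 value". An earlier run-in value enters only as a fallback: "If the pre-dose Day 1 value is missing, the most recent pre-dose, non-missing value on or after the Day -14 visit" is then used. SAP 8.3.1.3 fits treatment, visit, their interaction, age group and genotype group, "with baseline ppFEV 1 and baseline SwCl as continuous covariates". The Protocol fixes the same list, in the synopsis ("with continuous baseline ppFEV 1 , continuous baseline SwCl, age at screening") and in 12.3.3.1 ("genotype group (F/F, F/G, F/RF, TCR/non-F) as covariates").

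The second run-in measurement exists. Protocol Table 3-2 schedules in-clinic spirometry at Day -14 (window Day -15 to Day -3) and again at Day 1. Protocol 9.1.2 gives its purpose: "The Day -14 clinic spirometry and SwCl assessments will be used for stratification of randomization". Neither the continuous Day -14 value nor its <70/≥70 stratum is in the model. For sweat chloride, SAP 8.1 does use two run-in values, by averaging the two most recent.

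**The concern.** A single spirometry result contains visit-to-visit noise. With Day 1 as the only ppFEV1 covariate, the noise in that reading stays partly in the residual variance of the change score. A second pre-randomisation reading on the same treatment helps to separate a subject's stable level from the noise of one day. Because it precedes randomisation, adjusting for it adds no bias and leaves the estimand and the margin unchanged.

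What is at stake is precision. The same 95% CI serves the non-inferiority test and then the superiority reading, for which neither document states a power.

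**Working it through.** **1. The plan's own figure.** Inputs from Protocol 12.1 and SAP 6.2.1: 275 per arm, 10% drop-out, SD 8, margin 3, true difference 0, 1-sided 0.025.
- Evaluable per arm: 275 × 0.9 = 247.5, taken as 248 (247 changes no figure by more than 0.2 points).
- SE = 8 × √(2/248) = 0.718. Noncentrality = 3/0.718 = 4.18. Power from the noncentral t = 98.6%, so more than 95% is confirmed.
- CI half-width = 1.965 × 0.718 = 1.41.

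**2. Formula for the gain.** Let V1 be the residual variance of the Week 16/24 mean given Day 1, and V2 the same given Day 1 and Day -14. CI narrowing = 1 − √(V2/V1).

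**3. Upper end: all visit variation is independent noise.** Let B be the between-subject variance (assumed) and w the noise variance per visit.
- The variance of (mean of two visits − Day 1) is 1.5w. Setting it to 8² = 64 gives w = 42.7, an SD of about 6.5.
- V1 = B + w/2 − B²/(B + w). V2 = B + w/2 − B²/(B + w/2).
- With an assumed subject SD of 15 (B = 225): V1 = 246.3 − 189.1 = 57.2; V2 = 246.3 − 205.5 = 40.8; ratio 0.714; narrowing 15.5%.
- Subject SD 12 gives 14.2% and subject SD 20 gives 16.7%.

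**4. Lower end.** If deviations are purely serial (first-order), Day -14 adds nothing once Day 1 is known, and the narrowing is 0%.

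**5. Range between.** 270 assumed settings were computed for the planned model (one covariate slope common to all visits). They combine subject SD 12, 15 or 20; an exponentially correlated component with a time constant of 14 to 240 days; a share of independent noise; and a Day -14 test at Day -15, -14 or -3. The SD of change is held at 8.

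| Share of independent visit noise | CI narrowing |
|---|---|
| none | 0% to 10.5% |
| 10% | 1.1% to 11.1% |
| 25% | 2.9% to 12.1% |
| 50% | 6.4% to 13.6% |
| 75% | 10.2% to 15.1% |
| 100% | 14.2% to 16.7% |

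The variance reduction runs from 0.03% to 30.6% (0.09% to 30.6% with visit-specific slopes). No setting gives a loss.

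**6. Effect on decisions** (248 per arm). The first figure takes 8 as the residual SD. The second takes 8 as the unadjusted SD and assumes 7.6 for the planned model; the settings above give 7.37 to 7.95. The true differences of -1 and +1.5 are illustrations and are not in the documents.

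| Variance reduction | CI half-width | NI power at 0 | NI power at -1 | Superiority power at +1.5 |
|---|---|---|---|---|
| 0% | 1.41 / 1.34 | 98.6% / 99.2% | 79.3% / 83.3% | 54.9% / 59.2% |
| 5% | 1.38 / 1.31 | 99.0% / 99.4% | 81.3% / 85.1% | 57.1% / 61.4% |
| 15% | 1.30 / 1.24 | 99.5% / 99.7% | 85.4% / 88.7% | 61.8% / 66.2% |
| 30% | 1.18 / 1.12 | 99.9% / 99.9% | 91.3% / 93.8% | 70.2% / 74.6% |

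Variance reductions of 5%, 15% and 30% correspond to CI narrowing of 1 − √0.95 = 2.5%, 1 − √0.85 = 7.8% and 1 − √0.70 = 16.3%.

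**7. Imperfect Day -14 data.** This was simulated with ANCOVA on the Week 16/24 mean at one mid-range setting (subject SD 15, time constant 60 days, 50% independent noise), where the base-case narrowing is 8.4%. The combined case has 40% of subjects lower at Day -14 by 4 points on average, bronchodilator mismatch in 5%, Day -14 missing in 5% and Day 1 missing in 2%. Narrowing is then 6.1%, coverage 95.0% (94.9% for the planned model) and bias -0.002 points.

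**The case against.** The strongest case against is materiality. Protocol and SAP agree on the covariate list, one pre-dose baseline covariate is a legitimate choice, and the trial is planned for non-inferiority at a true difference of 0, where power moves only from 98.6% to at most 99.9%. The larger gains need true differences that the plan does not assume. All of this stands, and it is why the point is optional.

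The size is also open. The top of the range needs every bit of visit variation to be independent noise, with an SD of about 6.5 at each visit. Subjects not on a modulator before the run-in (allowed by Protocol 8.1, criterion 6) have had only about two weeks of ELX/TEZ/IVA at Day -14, which weakens the correlation with later values. Step 7 suggests that such departures shrink the gain but do not remove it, though at one chosen setting only.

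The change could also spread. SAP 8.3.1.3 is the template for the sweat chloride, CFQ-R, BMI, BMI z-score and weight models, so an unqualified new term would carry into them by cross-reference. That objection is sound, and the fix limits the scope.

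A reader might infer from the sweat chloride baseline that ppFEV1 is handled inconsistently and should be averaged too. The documents do not support that. Different baselines for different endpoints are not a contradiction, and swapping in the average as covariate while still subtracting Day 1 would do harm (see the fix).

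**Conclusion.** The point holds as an optional precision improvement. Adding Day -14 clinic ppFEV1 would narrow the primary 95% CI by about 0% to 17%: roughly 0% to 11% with no independent visit noise, 6% to 14% with half, and 14% to 17% with all. These ranges rest on assumed subject SDs and correlation structures. The relative gains hold under either reading of SD 8; the absolute half-widths and powers do not carry over.

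Two stronger readings should be resisted. One is that the primary analysis is biased, invalid or underpowered: it adjusts for a proper baseline, and its stated power reproduces. The other is that a gain near 17% can be expected: the documents contain nothing that places this trial at the upper end rather than near zero.

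**What to change.** Before database lock and unblinding:

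- Keep Day 1 ppFEV1 as the subtracted baseline and as a covariate. Add continuous Day -14 clinic ppFEV1 as a further covariate in the ppFEV1 models only: the primary analysis, its supplementary and subgroup versions, and ppFEV1 through Week 52.
- State that the term does not carry over to the sweat chloride, CFQ-R, BMI, BMI z-score or weight models that refer to SAP 8.3.1.3.
- Define the value as the scheduled Day -14 clinic test (window Day -15 to Day -3). If it is missing or invalid, impute it by regression on Day 1 ppFEV1, pooled over arms and without post-baseline data, so that no subject is dropped. Subjects whose baseline falls back to the Day -14 value need no special rule; in simulation it made no difference (8.2% narrowing either way).
- Do not use the Protocol 9.2 stratification fallback as the covariate. It could be the Screening value, which precedes the run-in and may be post-bronchodilator.
- Do not replace the Day 1 covariate with the Day -14/Day 1 mean while still subtracting Day 1; residual variance then rises by up to about 13%.
- Record the change in SAP 2.1 ("Modifications to the Approved Clinical Study Protocol", now marked as not applicable), or amend the protocol, which fixes the covariate list.

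Cost: about one degree of freedom and a SAP amendment, with no new data. If the true gain is nil, the CI was 0.05% to 0.09% wider in simulation.
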